Appendix and moved list of abbreviations		
Removed reference to GBT021601-012 participants enrolling	GBT021601-012 study is complete, and participants will not be enrolling in C5351005	2.1 SoA; 3.2 Benefit/Risk Assessment; 5.1 Overall Design; 5.3 Justification for Dose; 9.2 Efficacy Assessments; 11.3 Detailed Dosing Information for Osivelotor
Updated visit window after 24 weeks from +/-4 weeks to +/- 14 days	To preserve drug supply	2.1 SoA Table 1, Table 2, Table 3, Table 4
Updated status of GBT021601-011 and GBT021601-012 to completed	To reflect completion of studies.	3.1 Background
Updated IB provided	Reflects 2023 approved version	3.1 Background; 12 References
Removed “at approximately 60 global clinical sites” and updated to “will have a global distribution”.	To align with Pfizer standards for interventional trials	5.1 Overall Design
Replaced “male or female” in inclusion criteria.	More inclusivity	6.1 Inclusion Criteria
Combined overdose into single section and revised instructions for reporting overdose. Revised guidance for Concomitant Medications and Procedures and added appendix for Prohibited Concomitant Medications That May Result in DDI. Added new sections on Potential Cases of Acute Kidney Injury and Drug-induced Liver Injury. Updated guidance for calculating eCrCl or eGFR. Added appendix for Kidney Safety. Added clarifying text to Liver Safety appendix. Added serum cystatin C, haptoglobin, hemopexin, and	To align with Pfizer safety guidance for interventional trials	7.6. Treatment of Overdose; 7.7 Concomitant Medications and Procedures; 8.2.1 Potential Cases of Acute Kidney Injury; 9.3.3 Clinical Laboratory Tests; 9.4.9 Drug-induced Liver Injury; 11.4 Liver Safety: Suggested Actions and Follow-Up Assessments; 11.5 Kidney Safety Monitoring Guidelines; 11.6 Prohibited and Restricted Concomitant Medications That May Result in DDI

Description of Change	Brief Rationale	Section # & Name
soluble C3 collection to laboratory tests.		
Deleted redundant 'Reporting Pregnancy' section and updated 'Exposure During Pregnancy' section. Updated guidance for 'Exposure During Breastfeeding'.	To align with Pfizer standards for interventional trials	Deleted previous 8.4.7 Reporting Pregnancy; 9.4.13.1 Exposure During Pregnancy; 9.4.13.2 Exposure During Breastfeeding
Revised/refined pharmacodynamics/biomarkers	To reflect updated study design	9.7 Pharmacodynamics/Biomarkers

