**Adult Participants from Part A of C5351004 and Other Applicable Osivelotor Open Label Studies with no Delay of Start**

**Table 2. Schedule of Assessments for Adult Participants from Part A of C5351004 and Other Applicable Osivelotor Open Label Studies with no Delay of Start**

	Treatment Period				
Study Week	Baseline visit	12	24	Every 12 weeks	EOS k /ET
Study Day	1 (± 30)	84 (± 7)	168 (± 7)	252+ (± 14 Days)	
Informed consent/assent	X				
Eligibility assessment	X				
Medical history	X				
Physical examination a	X	X	X	X	X
Height	X				
Weight	X	X	X	X	X
Vital signs b	X	X	X	X	X
Serology (hepatitis A, B, C, HIV) only if clinically indicated	X				
Hematology including reticulocyte count and serum chemistry		X	X	X	X
aPTT, INR, PT	X				
Serum erythropoietin	X	X	X	X	X
eGFR (for adults, children or infants) or eCrCl (adolescents) c	X		X	X	X
Urinalysis	X	X	X	X	X
Pregnancy test (for females, post menarche) d	X	X	X	X	X
Contraception check i	X	X	X	X	X

**Table 2. Schedule of Assessments for Adult Participants from Part A of C5351004 and Other Applicable Osiveltor Open Label Studies with no Delay of Start**

	Treatment Period				
Study Week	Baseline visit	12	24	Every 12 weeks	EOS k /ET
Study Day	1 (± 30)	84 (± 7)	168 (± 7)	252+ (± 14 Days)	
PK samples (whole blood and plasma) e	X	X	X	X	X
RBC deformability and RBC mitochondrial content (at sites where available) f,j	X	X	X	X	X
Flow adhesion f,j	X	X	X	X	X
Peripheral blood smear f,j	X	X	X	X	X
Exploratory Biomarkers 	X	X	X	X	X
PGI-C/CGI-C f	X	X	X	X	X
PGI-S/CGI-S f	X	X	X	X	X
PROMIS SF Fatigue 13a, SF Pain Interference 8a, and NRS Pain Intensity f	X	X	X	X	X
EQ-5D-5L f	X	X	X	X	X
WPAI+CIQ:SCD f	X	X	X	X	X
Qualitative interview f,g	X				
Study drug administration	←-----→				
Dispense study drug	X	X	X	X	
Return unused study drug h		X	X	X	X
Concomitant medication	X	X	X	X	X
Serious and nonserious AE monitoring	X	X	X	X	X

**Table 2. Schedule of Assessments for Adult Participants from Part A of C5351004 and Other Applicable Osiveltor Open Label Studies with no Delay of Start**

	Treatment Period				
Study Week	Baseline visit	12	24	Every 12 weeks	EOS k /ET
Study Day	1 (± 30)	84 (± 7)	168 (± 7)	252+ (± 14 Days)	

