### Adult Participants

	AKI (including DIKI) Any one of the below	DICI
Scys & Screat	Simultaneous, confirmed serum cystatin C (Scys) increase and confirmed Screat increase	Confirmed Screat increase without confirmed increase in reflex Scys AND
eGFR	Decrease in Screat-based eGFR and combined Screat-Scys-based eGFR (when available)	Confirmed Screat-based eGFR decrease without confirmed combined Screat-Scys-based eGFR decrease.
Albuminuria or proteinuria	Confirmed albuminuria increase (see Section 11.5 for Grades A1 to A3 quantitation)	
Urine volume	Urine volume <0.5 mL/kg/h for 6 consecutive hours	

Regardless of the presence or absence of increase in Screat, DIKI and other causes of AKI may be suspected if either (i) new-onset or worsening albuminuria or proteinuria are detected or (ii) urine volume (if measured) is <0.5 mL/kg/h for 6 consecutive hours.

All confirmed cases of clinically relevant decrease in kidney function should be considered potential cases of DIKI if no other reason for the kidney function abnormalities has been found.

See [Appendix 2: Liver Safety: Suggested Actions and Follow-Up Assessments](#) for instructions for laboratory testing to monitor kidney function and reporting laboratory test abnormalities.

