**Table 9. Clinical Safety and Other Laboratory Tests**

Hematology	Chemistry	Urinalysis	Other
Hematocrit	ALT	Albumin	EPO
Hb	Albumin	Bilirubin	FSH (postmenopausal females only)
RBC count	Alkaline phosphatase	Blood	Pregnancy –serum and urine (females who are post menarche and of child-bearing potential) b
Mean corpuscular volume	AST	Creatinine	
Mean corpuscular Hb	Bicarbonate	Glucose	
Mean corpuscular Hb concentration	Blood urea nitrogen	Ketones	
Reticulocyte count (absolute and %)	Calcium	Leukocytes	
Platelet count (estimate not acceptable)	Chloride	Microscopic analysis of sediment if clinically indicated	RBC deformability
White blood cell count including differential count (percent and absolute):	Creatine phosphokinase	Nitrite	Flow Adhesion
Neutrophils	Creatinine	pH	RBC Mitochondrial Content
Lymphocytes	Fasting glucose	Protein	Peripheral Smear
Monocytes	Globulin	Specific gravity	Serum cystatin C
Basophils	Lactate dehydrogenase	Urobilinogen	Haptoglobin
Eosinophils	Magnesium		Hemopexin
PT	Phosphorous		Soluble C3
aPTT	Potassium		
INR	Sodium		
	Total bilirubin (direct and indirect)		Serology Panel (if clinically indicated):
	Total protein		HIV antibody
	Uric acid		Hepatitis A virus IgM antibody
	eGFR a		Hepatitis B virus surface antigen
			Hepatitis C virus antibody

Abbreviations: ALT, alanine aminotransferase; aPTT, activated partial thromboplastin time; AST, aspartate aminotransferase; CKD-EPI, chronic kidney disease epidemiology; eGFR, estimated glomerular filtration rate; EPO, erythropoietin; FSH, follicle stimulating hormone; Hb, hemoglobin; HIV, human immunodeficiency virus; IgM, immunoglobulin M; INR, International Normalized Ratio; PT, prothrombin time; RBC, red blood cells.

a Using CKD-EPI equations (for adults 18 years and above), Cockcroft-Gault formula (for adolescents 12 to <18 years), Modified Schwartz Equation (for children 2 to <12 years), or Schwartz equation (for infants 6 months to <2 years), see Section 11.5.2.

b Tests will be conducted at the clinic.

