## 11.5. Appendix 3: Kidney Safety Monitoring Guidelines

### 11.5.1. Laboratory Assessment of Change in Kidney Function and Detection of Kidney Injury

Standard kidney safety monitoring requires assessment of baseline and postbaseline Screat measurement to estimate kidney function [Screat-based eGFR] or creatinine clearance [eCrCl]. Baseline and postbaseline Scys makes it feasible to distinguish AKI from other causes of Screat increase. If Screat increase is confirmed after baseline, then reflex measurement of Scys is indicated.

**ADULTS:** Currently, 2021 CKD-EPI eGFR equations (Screat-only based and combined Screat plus Scys-based) are valid for use in adults only. At baseline Screat and Scys values are needed to calculate 2021 CKD-EPI eGFR by Screat-only based equation (see Table in Section 11.5.2.1) and by combined Screat plus Scys-based equation. When post-baseline Screat increase  $\geq 0.3$  mg/dL is confirmed, then reflex Scys measurement is needed to enable post-baseline comparison of eGFR changes (Screat-only based eGFR and combined Screat plus Scys eGFR).

**PEDIATRICS:** Currently, no Screat plus Scys eGFR equations have been universally adopted for pediatrics. Therefore, comparison of baseline Screat and Scys to post-baseline Screat and reflex Scys are utilized to support differentiation of AKI from DICI.

Regardless of whether kidney function monitoring tests are required as a routine safety monitoring procedure in the study, if the investigator or sponsor deems it necessary to further assess kidney safety and quantify kidney function, then these test results should be managed and followed per standard of care.

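### The kidney-injury rule needs a baseline serum cystatin C that no visit schedule collects, so an adult creatinine rise can fit both the injury and the benign column.

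*Protocol*

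**What the plan says.** **Why a baseline is wanted.** Protocol Section 11.5.1 gives the principle: "Baseline and postbaseline Scys makes it feasible to distinguish AKI from other causes of Screat increase". For adults it adds "At baseline Screat and Scys values are needed to calculate 2021 CKD-EPI eGFR by Screat-only based equation", and the same sentence goes on to the combined creatinine-cystatin equation. For children, "comparison of baseline Screat and Scys to post-baseline Screat and reflex Scys are utilized to support differentiation of AKI from DICI". The only trigger it gives for a later cystatin C is a reflex test: "If Screat increase is confirmed after baseline, then reflex measurement of Scys is indicated".

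**How the result is used.** Section 8.2.1 has one table for children and one for adults. Any one row is enough for AKI. The first limb of DICI is "Confirmed Screat increase without confirmed increase in reflex Scys". For adults a second limb must also hold: a confirmed fall in creatinine-based eGFR without a confirmed fall in combined eGFR.

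**When the test is drawn.** Table 9 lists "Serum cystatin C" in its column of other tests, with no timing note. Section 9.3.3 refers timing to the Schedule of Assessments (SoA, Section 2.1). SoA Tables 1 to 4 have no cystatin C row. In Table 2 the row "Hematology including reticulocyte count and serum chemistry" is not marked at Baseline; the same holds in Tables 3 and 4, while Table 1 does mark it.

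**The concern.** A rule that asks whether a marker rose needs a reference value. Section 11.5.1 recognises this, but the schedule that sites follow does not collect one. A site that does exactly what the SoA asks will reach a creatinine rise, draw the reflex cystatin C, and have no documented earlier value to set it against.

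The label matters for the individual participant's work-up and for what is recorded. Section 9.4.7.1 asks for a known diagnosis rather than the separate signs. In Section 11.5.4, AKI has no Grade 1 or 2, whereas increased creatinine starts at Grade 1. The same laboratory picture can therefore be recorded under different terms and grades, depending on how the site reads an incomplete comparison.

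**Working it through.** The plan states no figure on this point. The check is a comparison of passages, followed by an illustration with the protocol's own equations.

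**Step 1. Schedule against requirement (Section 2.1 against 11.5.1)**

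| Item | Table 1 | Table 2 | Table 3 | Table 4 |
|---|---|---|---|---|
| Cystatin C, any visit | no row | no row | no row | no row |
| eGFR or eCrCl at Baseline | yes | yes | yes | yes |
| Serum chemistry at Baseline | yes | no | no | no |
| Serum erythropoietin at Baseline | yes | yes | yes | yes |

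Cystatin C is scheduled in 0 of 4 tables. The biomarker footnotes name haptoglobin, hemopexin and soluble C3 as examples, not cystatin C. The eGFR footnotes that cover adults name the 2021 CKD-EPI equations, and Section 11.5.2.1 gives a creatinine-only form that meets that wording without cystatin C.

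**Step 2. Classify a confirmed creatinine rise with no baseline Scys (Section 8.2.1)**

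- *Adult, DICI column.* No Scys increase from baseline can be confirmed, so the first limb is met. No combined-eGFR decrease from baseline can be confirmed, so the second limb is met too, given the creatinine-based fall.
- *Adult, AKI column.* The eGFR row asks for a fall in creatinine-based eGFR and, only where it is available, in combined eGFR. The first has occurred and the second is unavailable, so the row can be read as met. The same case fits both columns.
- *Child.* There is no eGFR row. Without albuminuria or low urine volume, only the DICI column fits.

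**Step 3. Can the event sample alone settle it?**

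Combined equation for men, Section 11.5.2.1: eGFR = 135 × (Screat/0.9)^a × (Scys/0.8)^b × 0.9961^age, with a = -0.144 if Screat ≤ 0.9 and -0.544 above, and b = -0.323 if Scys ≤ 0.8 and -0.778 above.

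Assumed for illustration, not from the documents: man aged 30, Screat 0.8 rising to 1.2 mg/dL (1.5-fold), event Scys 0.9 mg/L.

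- Event: 135 × (1.2/0.9)^-0.544 × (0.9/0.8)^-0.778 × 0.9961^30 = 93.7
- Baseline Scys 0.7: 135 × (0.8/0.9)^-0.144 × (0.7/0.8)^-0.323 × 0.9961^30 = 127.5; change 93.7/127.5 - 1 = -26.5%
- Baseline Scys 0.9: 111.4; change -15.9%
- Baseline Scys 1.1: 95.3; change -1.7%

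With a smaller rise, 0.8 to 1.1 mg/dL, the three changes are -23.0%, -11.8% and +3.0%. One event value is compatible with a large fall or with almost none.

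**Step 4. Would a baseline sample be enough?**

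Not by itself. Section 8.2.1 defines a confirmed creatinine increase but not a confirmed cystatin increase. The combined equation also contains creatinine. Over the assumed cases (a woman with Screat 0.6 and men with 0.8 and 1.0 mg/dL, all aged 30, rising by 0.3 mg/dL or 1.5-fold), combined eGFR falls by 12% to 20% with Scys unchanged, and creatinine-only eGFR falls by 24% to 39%. The adult eGFR row gives no size at which a fall counts.

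**The case against.** **Cases go to the benign category.** A reader might infer that, without a baseline, true injury is filed as DICI. For adults the documents do not support this. Any one AKI row suffices, the combined eGFR counts only where available, and albuminuria or low urine volume qualifies without cystatin C. Section 8.2.1 also closes by treating unexplained confirmed declines as potential drug-induced kidney injury. It describes differentiation as a clinical work-up that may include imaging, histopathology and nephrology advice. What remains for adults is two possible answers, not a lean to the benign one. The one-sided result belongs to the pediatric table, and SAP Section 2.2.3 says that only adults from Part A of C5351004 were enrolled.

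**Half the adult AKI criteria are unusable.** This might be inferred because two of the four rows mention cystatin C. Only the row on simultaneous cystatin and creatinine increases depends strictly on a cystatin change; the eGFR row can still be applied.

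**The baseline may exist elsewhere.** SoA notes let parent end-of-treatment (EOT) assessments serve as Baseline and ask for missing ones to be completed on Day 1. This explains the absence of Baseline chemistry in Tables 2 to 4. It does not show that cystatin C was among the parent assessments, and Day 1 additions are again those in the SoA. If Day 1 falls more than 7 days after the parent study, new Baseline assessments are required, so an EOT value would not serve the delayed starters in Table 1 (more than 42 days).

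**The primary endpoint is affected.** This might be inferred because laboratory change is primary. The SAP summarises laboratory values as numbers (Sections 3.1.2 and 6.1.2) and plans no AKI-versus-DICI table.

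**Everyone enrolled before the test was introduced is affected.** The Amendment 4 change summary ("Added serum cystatin C, haptoglobin, hemopexin, and") dates the test's entry into the laboratory list to 08 Feb 2024; the original protocol is dated 09 May 2022. Those dates do not say how many participants had started, and the documents give no count.

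Two parts of the other side stand. The SAP, dated 23 Jun 2025, speaks of enrolment in the past tense, so a new Baseline row may reach few participants. Serial samples after an event could also still show a rising cystatin C, though not a rise from baseline.

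**Conclusion.** The protocol contradicts itself. Section 11.5.1 calls for a baseline cystatin C in adults and children, Section 8.2.1 relies on the comparison, and Section 2.1 schedules the test nowhere. Followed as written, the adult rule can return both AKI and DICI for one case, and the pediatric rule returns only DICI when albuminuria and low urine volume are absent.

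The consequence is limited to investigator work-up and the term and grade recorded for individual events. The number of participants affected cannot be derived. The conclusion assumes that parent EOT data do not include cystatin C, or are not meant to be used for it; the documents are silent on both. The percentage changes are illustrations on assumed values and show only that an event sample cannot replace a baseline. The point merits correction because the plan's own safety rule does not work without it.

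**What to change.** - **Reconcile Section 2.1 with Section 11.5.1.** Add serum cystatin C to the Baseline column of SoA Tables 1 to 4, or state that a parent EOT cystatin C value serves as baseline and for whom. In Tables 2 to 4 the sample could come from serum drawn at Baseline for erythropoietin or eGFR, since no chemistry is marked there.
- **Participants already enrolled.** Label any cystatin C obtained later as an on-treatment reference, not as a baseline.
- **Reconcile Section 8.2.1 with Section 11.5.1.** The sponsor should state what counts as a confirmed cystatin increase and how a case without a baseline value is handled. The content of that clinical rule is for the sponsor to decide; this review proposes none.

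Cost: one row in each SoA table, or one sentence naming the parent source, and one additional central-laboratory assay per participant.

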### 11.5.2. Age-Specific Kidney Function Calculation Recommendations

At Screening, eGFR will be calculated using 2021 CKD-EPI eGFR equations (for adults 18 years and above), eCrCl will be calculated using Cockcroft-Gault formula (for adolescents 12 to <18 years), and eGFR will be calculated using Modified Schwartz Equation (for children 2 to <12 years), or Bedside Schwartz equation (for infants 6 months to <2 years).

#### 11.5.2.1. Adults (18 Years and Above)—2021 CKD-EPI Equations (Inker, Eneanya et al. 2021)

eGFR (mL/min/1.73m^2)

2021 CKD-EPI Screat Only	Screat (mg/dL)	Scys (mg/L)	Recommended eGFR Equation
Female	if $\leq 0.7$	NA	$eGFR = 143 \times (Screat/0.7)^{-0.241} \times (0.9938)^{Age}$
Female	if $> 0.7$	NA	$eGFR = 143 \times (Screat/0.7)^{-1.200} \times (0.9938)^{Age}$
Male	if $\leq 0.9$	NA	$eGFR = 142 \times (Screat/0.9)^{-0.302} \times (0.9938)^{Age}$
Male	if $> 0.9$	NA	$eGFR = 142 \times (Screat/0.9)^{-1.200} \times (0.9938)^{Age}$
2021 CKD-EPI Screat-Scys Combined	Screat (mg/dL)	Scys (mg/L)	Recommended eGFR Equation

Female	if $\leq 0.7$	if $\leq 0.8$	$eGFR = 130 \times (Screat/0.7)^{-0.219} \times (Scys/0.8)^{-0.323} \times (0.9961)^{Age}$
Female	if $\leq 0.7$	if $> 0.8$	$eGFR = 130 \times (Screat/0.7)^{-0.219} \times (Scys/0.8)^{-0.778} \times (0.9961)^{Age}$
Female	if $> 0.7$	if $\leq 0.8$	$eGFR = 130 \times (Screat/0.7)^{-0.544} \times (Scys/0.8)^{-0.323} \times (0.9961)^{Age}$
Female	if $> 0.7$	if $> 0.8$	$eGFR = 130 \times (Screat/0.7)^{-0.544} \times (Scys/0.8)^{-0.778} \times (0.9961)^{Age}$
Male	if $\leq 0.9$	if $\leq 0.8$	$eGFR = 135 \times (Screat/0.9)^{-0.144} \times (Scys/0.8)^{-0.323} \times (0.9961)^{Age}$
Male	if $\leq 0.9$	if $> 0.8$	$eGFR = 135 \times (Screat/0.9)^{-0.144} \times (Scys/0.8)^{-0.778} \times (0.9961)^{Age}$
Male	if $> 0.9$	if $\leq 0.8$	$eGFR = 135 \times (Screat/0.9)^{-0.544} \times (Scys/0.8)^{-0.323} \times (0.9961)^{Age}$
Male	if $> 0.9$	if $> 0.8$	$eGFR = 135 \times (Screat/0.9)^{-0.544} \times (Scys/0.8)^{-0.778} \times (0.9961)^{Age}$

#### 11.5.2.2. Adolescents (12 Years to <18 Years) — Cockcroft-Gault Formula

eCrCl (mL/min)

Males:  $eCrCl = [(140 - \text{age}) \times \text{body weight (in kg)}] / [Screat (\text{in mg/dL}) \times 72]$

Females:  $eCrCl = 0.85 \times [(140 - \text{age}) \times \text{body weight (in kg)}] / [Screat (\text{in mg/dL}) \times 72]$

#### 11.5.2.3. Children (2 Years to <12 Years) — (Modified) Schwartz Equation

eCrCl normalized to BSA (mL/min/1.73 m^2)

$eCrCl = (K \times Ht) / Screat$

Ht in cm; Screat in mg/dL.

K (proportionality constant): Female child <12 years: K = 0.55. Male child <12 years: K = 0.70.

#### 11.5.2.4. Infants (1 Month to <2 Years) and Neonates (<1 Month) — (Bedside) Schwartz Equation

$eGFR (\text{mL/min/1.73 m}^2) = 0.413 \times (Ht/Screat)$

Ht in cm; Screat in mg/dL.

#### 11.5.3. Kidney Function Calculation Tools

The sponsor has provided the following resources to investigational sites when required to calculate age-specific kidney function at Screening, Baseline, and post-Baseline visits. Site calculations of kidney function can be performed manually, using the age appropriate formulae (see Section 11.5.2) and can use recommended online kidney function calculators to reduce the likelihood of a calculation error.

The United States National Kidney Foundation Online Calculators.

- Adults (18 years and above) - 2021 CKD-EPI Creatinine Online Calculator (eGFR): [https://www.kidney.org/professionals/KDOQI/gfr\\_calculator](https://www.kidney.org/professionals/KDOQI/gfr_calculator)

- Adolescents (12 years to <18 years) - Cockcroft-Gault Formula (eCrCl):  
[https://www.kidney.org/professionals/kdoqi/gfr\\_calculatorCoc](https://www.kidney.org/professionals/kdoqi/gfr_calculatorCoc)

Investigational sites are responsible to ensure that the accurate age-specific equation is selected and that the correct units are used for serum creatinine (mg/dL only), serum cystatin C (mg/L only), total body weight (kg only), and age (years). Investigators are expected to (i) review and confirm correctness of the kidney function calculation results and (ii) evaluate the calculated value within the context of historical information available to them in the participant's medical record. Investigators are responsible for the clinical oversight of the participant eligibility process, kidney function calculation, and dose selection and adjustments per study protocol. Investigators are encouraged to direct questions or uncertainties regarding kidney function and dosing to the Pfizer Clinical Team and Medical Monitor, if needed.

#### 11.5.4. Adverse Event Grading for Kidney Safety Laboratory Abnormalities

AE grading for decline in kidney function (ie, eGFR or eCrCl) will be according to CTCAE criteria for both pediatric and adult participants.

CTCAE Term (2017)	Grade 1	Grade 2	Grade 3	Grade 4	Grade 5
AKI	NA	NA	Hospitalization indicated	Life-threatening consequences; dialysis indicated	Death
AKI: A disorder characterized by acute loss of kidney function (within 2 weeks) and is traditionally classified as pre-renal (low blood flow into kidneys), renal (kidney damage), or post-renal causes (ureteral or bladder outflow obstruction).					
Creatinine increased	>ULN to 1.5 x ULN	>1.5 to 3.0 x baseline OR >1.5 to 3.0 x ULN	>3.0 to 6.0 x baseline OR >3.0 to 6.0 x ULN	>6.0 x ULN	NA
CKD	eGFR $\geq 60$ to 89 mL/min/1.73m  OR eCrCl $\geq 60$ to 80 mL/min	eGFR 30 to 59 mL/min/1.73m  OR eCrCl 30 to 59 mL/min	eGFR 15 to 29 mL/min/1.73m  OR eCrCl 15 to 29 mL/min	eGFR <15 mL/min/1.73m  OR eCrCl <15 mL/min OR dialysis indicated	Death
Proteinuria	ADULTS: Proteinuria 1+ OR Proteinuria >0.5 to <1.0 g/24 h	ADULTS: Proteinuria 2+ or 3+ OR Proteinuria 1.0 to <3.5 g/24 h PEDIATRICS: Urine Protein-	ADULTS: Proteinuria 4+ OR Proteinuria $\geq 3.5$ g/24 h PEDIATRICS: Urine Protein-to-Creatinine	NA	NA

CTCAE Term (2017)	Grade 1	Grade 2	Grade 3	Grade 4	Grade 5
		to-Creatinine Ratio (UPCR) 0.5 to 1.9	Ratio (UPCR) >1.9		

CKD: A disorder characterized by gradual and usually permanent loss of kidney function resulting in kidney failure.

